 - If a scan within the first 4 months exists and shows progressive disease the patient is not eligible (i.e. the scan result cannot be overruled by Investigator assessment of clinical benefit).
 - Should a subsequent scan for the same line of treatment show clinical benefit after initial radiographic progression (i.e. pseudoprogression) the patient is eligible.
- 27. Patients should have had only one CPI and one platinum based regimen, whether sequentially or concurrently. The acceptable sequences are:
 - Platinum-based chemotherapy (1L) + CPI treatment (1L); i.e., study treatment is second line therapy
 - Platinum-based chemotherapy (1L) → CPI treatment (2L); i.e., study treatment is third line therapy
 - CPI treatment (1L) → Platinum-based chemotherapy (2L); i.e., study treatment is third line therapy
 - Adjuvant chemo-radiation treatment with anti-PD-1/PD-L1 inhibitors or consolidation treatment with anti-PD-1/PD-L1 after definitive chemo-radiation therapy is allowed but participants do require an additional line of anti-PD-1/PD-L1 treatment in the metastatic setting.

Specific Inclusion Criteria for Part B3 Expansion in PD L1 High, CPI Naïve, First Line NSCLC Cohort

28. Participants with histologically confirmed advanced NSCLC with PD-L1 high defined as ≥ 50% PD-L1 expression based on immunohistochemistry using antibody clone 22c3, sp263 or 28-8. Expression will be determined in a fresh tumor biopsy collected during study screening or a possibly available archival sample, provided that the latter is not older than 12 months and has been obtained after failure of last CPI treatment line and prior to receiving study treatment.

Specific Inclusion Criteria for Part B4 Expansion in CPI-Naïve SCLC Cohort

- 29. Participants must have histologically confirmed SCLC.
- 30. Participants may have had prior chemotherapy, radiation therapy or declined approved therapies for SCLC.

Additional Inclusion Criteria for Part B5: CPI Naïve Esophageal Squamous Cell Carcinoma

- 31. Participants whose major lesion was histologically confirmed squamous cell carcinoma or adenosquamous cell carcinoma of the esophagus.
- 32. Patients who have previously received not more than 1 prior lines of treatment for metastatic disease prior to enrolling to the study. The prior line must be a fluoropyrimidine and platinum-based regimen and patients must have experienced progressive disease.

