Any medication or vaccine (including over-the-counter [OTC] or prescription medicines, approved dietary and herbal supplements, nutritional supplements) used by a participant during screening until the follow-up visit must be recorded along with reason for use, dates of administration (including start and end dates) and dosage information (including dose and frequency). The Medical Monitor *can advise if* there are any questions regarding concomitant or prior therapy.

All concomitant medications *or vaccines* should be reported to the Investigator and recorded on the Concomitant Medications electronic Case Report Form (eCRF). All therapy and/or medication administered to manage adverse events should be recorded on the Adverse Event eCRF.

Radiotherapy

The use of limited field palliative radiotherapy is allowed at any time during the study, **except for:**

- Days where RO7121661 is administered.
- During the DLT evaluation window.
- If radiotherapy is administered during the DLT evaluation window, the participant will not be evaluable.

Prohibited Therapy

All medications (prescription and OTC) taken within 30 days of study screening will be recorded on the appropriate eCRF. As a general rule, no concomitant medication will be permitted, with the exception of medications to treat AEs and therapy for pre-existing conditions, unless the rationale for exception is discussed and clearly documented.

Use of the following therapies is prohibited during the study and for at least 28 days or 5 half-lives of the drug, whichever is shorter, prior to initiation of study treatment, unless otherwise specified below:

Investigational or unlicensed/unapproved agents

Immunotherapy/radio-immunotherapy

Chemotherapy / targeted therapy

Radiotherapy (with the exception of limited field palliative radiotherapy).

Biologic agents (e.g., bevacizumab, cetuximab).

[figure not shown]
Chronic use of steroids (inhaled and topical steroids are permitted) at baseline of > 10 mg of prednisone/day (or equivalent). Concurrent high doses of systemic corticosteroids will not be allowed.

Administration of a live, attenuated vaccine within 28 days before Cycle 1 Day 1 or anticipation that such a live attenuated vaccine will be required during the study.

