- 6. Tumor assessments will include contrast-enhanced computed tomography (CT) and/or magnetic resonance imaging (MRI) of the chest, abdomen, and pelvis as well as the site of the primary tumor (if applicable). Measurable lesions will be assessed at Screening and then every 8 weeks (±7 days) after Cycle 1, Day 1 for the first year; and every 12 weeks (±7 days) thereafter until disease progression or treatment discontinuation (whichever occurs last), initiation of a new line of therapy or death. Tumor assessments performed as standard of care prior to obtaining informed consent and within 28 days of Cycle 1, Day 1 may be used as the screening tumor assessment rather than repeating the scans. Evaluation of tumor response will be based on RECIST v1.1 criteria (see Appendix 7). Every time a tumor assessment is done, a PD Serum sample should be collected.

Table 1 Schedule of Activities: Q2W regimen for Part A and B1, 2, 3, 4, and 5 (cont.)

- 7. The auto-antibody panel will be assessed at Screening, pre-dose Cycles 3 and 9, and every 6 cycles thereafter. In participants who develop signs and/or symptoms suggestive of auto-immune disease while on-treatment, the auto-antibody panel (anti-nuclear antibody, anti-double-stranded deoxyribonucleic acid (DNA), circulating anti-neutrophil cytoplasmic antibody [cANCA], and perinuclear anti neutrophil cytoplasmic antibody [pANCA]) should be repeated. Patients with confirmed positive serology of at least one of the auto-antibody panel during the course of the study should be discussed between Sponsor and Investigators, and if judged clinically relevant, could be referred to a specialist to exclude an underlying auto-immune disease.
- 8. Serology (as per local regulations) includes HIV, hepatitis B surface antigen, total hepatitis B core antibody, hepatitis C virus antibody. Results must be obtained and reviewed prior to administration of RO7121661.
- 9. Coagulation sampling (including prothrombin time [PT], international normalized ratio [INR], and activated partial prothrombin time [aPTT]) will be performed at the specified time-points (prior to dosing). After Cycle 6, coagulation sampling will be performed at every visit when tumor assessment is performed. Additional coagulation parameters (i.e., anti-thrombin III, fibrinogen, PT, fibrin degradation products, D-dimer) maybe be assessed according to clinical judgment.

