Although SCLC is more responsive to chemotherapy and radiation therapy than other types of lung cancer, a cure is difficult to achieve because SCLC has a greater tendency to be widely disseminated by the time of diagnosis (NIH National Cancer Institute 2016). At the time of diagnosis, approximately 30% of patients with SCLC will have tumors confined to the hemithorax of origin, the mediastinum, or the supraclavicular lymph nodes. These patients are designated as having limited-stage disease (LD), where the treatment goal is curative (Früh et al 2013). Patients with tumors that have spread beyond the supraclavicular areas are said to have extensive-stage disease (ED). The prognosis of SCLC strongly depends on the tumor stage, which is evaluated by the new tumor-node-metastasis (TNM) version 7 staging system according to the Union for International Cancer Control (UICC) (Früh et al 2013).

In the last 30 years, multiple therapeutic agents and strategies, including dose intensification, have been explored, but with marginal improvement in PFS, and significant toxicity. The most important advances have improved the precision of radiation therapy and have introduced better supportive care measures, such as more effective antiemetic regimens.

The generally accepted standard for first-line systemic therapy is etoposide combined with either cisplatin or carboplatin. Initial objective response rates of 60 to 80% are seen in patients without substantive co-morbid conditions. However, almost all patients with ED and most patients with LD experience disease progression within months of completing first-line therapy.

There is only one approved therapy for SCLC that has progressed on a platinum and etoposide combination regimen: topotecan, a topoisomerase 1 inhibitor. Recurrent/refractory SCLC is substantially less responsive to therapy than primary disease. Response rates for topotecan are approximately 25% for relapses occurring at least 3 months after completion of first-line therapy, and as low as 3 to 6% for progressive disease occurring at the time of or shortly after completion of first-line therapy. Objective responses to a third line of chemotherapy are uncommon.

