6.5.1 Permitted Therapy

Any medication or vaccine (including over-the-counter [OTC] or prescription medicines, approved dietary and herbal supplements, nutritional supplements) used by a participant during screening until the follow-up visit must be recorded along with reason for use, dates of administration (including start and end dates) and dosage information (including dose and frequency). The Medical Monitor *can advise* if there are any questions regarding concomitant or prior therapy.

All concomitant medications *or vaccines* should be reported to the Investigator and recorded on the Concomitant Medications electronic Case Report Form (eCRF). All therapy and/or medication administered to manage adverse events should be recorded on the Adverse Event eCRF.

Radiotherapy

Participants should not receive study treatment during radiation treatment.

The use of limited field palliative radiotherapy is allowed at any time during the study, **except for:**

- Days where RO7121661 is administered.
- During the DLT evaluation window.
 - If radiotherapy is administered during the DLT evaluation window, the participant will not be evaluable.

6.5.2 Prohibited Therapy

All medications (prescription and OTC) taken within 30 days of study screening will be recorded on the appropriate eCRF. As a general rule, no concomitant medication will be permitted, with the exception of medications to treat AEs and therapy for pre-existing conditions, unless the rationale for exception is discussed and clearly documented.

Use of the following therapies is prohibited during the study and for at least 28 days or 5 half-lives of the drug, whichever is shorter, prior to initiation of study treatment, unless otherwise specified below:

- Investigational or unlicensed/unapproved agents
- Immunotherapy/radio-immunotherapy
- Chemotherapy / targeted therapy
- Radiotherapy (with the exception of limited field palliative radiotherapy).
- Biologic agents (e.g., bevacizumab, cetuximab).
- Chronic use of steroids (inhaled and topical steroids are permitted) at baseline of >10 mg of prednisone/day or equivalent. Concurrent high doses of systemic corticosteroids will not be allowed.
- Administration of a live, attenuated vaccine within 28 days before Cycle 1 Day 1 or anticipation that such a live attenuated vaccine will be required during the study.

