1.2 TARGET LESIONS: SPECIFICATIONS BY METHODS OF MEASUREMENTS

1.2.1 Measurement of Lesions

All measurements should be recorded in metric notation, using calipers if clinically assessed. All baseline evaluations should be performed as close as possible to the treatment start and never more than 4 weeks before the beginning of the treatment.

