2.3.1. Evaluation of Target Lesions

Complete Response (CR): Disappearance of all target lesions. Any pathological lymph nodes (whether target or non-target) must have reduction in short axis to < 10 mm.

Partial Response (PR): At least a 30% decrease in the sum of diameters of target lesions, taking as reference the baseline sum diameters.

Progressive Disease (PD): At least a 20% increase in the sum of diameters of target lesions, taking as reference the smallest sum on study including baseline (nadir). In addition to the relative increase of 20%, the sum must also demonstrate an absolute increase of at least 5 mm. (Note: the appearance of one or more new lesions is also considered progression).

Stable Disease (SD): Neither sufficient shrinkage to qualify for PR nor sufficient increase to qualify for PD.

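### The RECIST baseline scan may predate a permitted last dose of chemotherapy or targeted therapy, so some carry-over can be scored as RO7121661 activity, mainly in Part B4 and Part A

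*Combined protocol and SAP*

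**What the plan says.** **Baseline scan.** Table 1, footnote 6 (Section 1.3): "Tumor assessments performed as standard of care prior to obtaining informed consent and within 28 days of Cycle 1, Day 1 may be used" instead of repeating the scan at screening. Table 1, footnote 1 and Section 8.10.1 say the same of standard-of-care tests in general. Appendix 7, Section 1.2.1 asks for baseline as near to treatment start as possible and "never more than 4 weeks before the beginning of the treatment". None of these mentions the last dose of earlier treatment.

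**Washout.** Section 1.1, repeated in Section 6.5.2: "Use of the following therapies is prohibited during the study and for at least 28 days or 5 half-lives of the drug, whichever is shorter". The list that follows includes "Chemotherapy / targeted therapy".

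**Scoring.** Appendix 7, Section 2.3.1 defines partial response as "At least a 30% decrease in the sum of diameters of target lesions, taking as reference the baseline sum diameters". ORR, DCR, DoR and PFS by RECIST 1.1 are the primary endpoints of Part B and secondary endpoints of Part A (Section 3, Table 4).

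**Entry to B4.** Sections 1.1 and 4.1 admit failure of, progression on, or intolerance to standard therapy. Criterion 30 adds: "Participants may have had prior chemotherapy, radiation therapy or declined approved therapies for SCLC". It does not ask for progression on the last regimen.

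**The concern.** The scan window is anchored to Cycle 1 Day 1 and the washout is anchored to the drug's half-life. Nothing orders the scan relative to the last prior dose. A participant could be scanned, receive a further dose of chemotherapy, and start RO7121661 within the rules. Any shrinkage from that dose would be measured against the older, larger sum.

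The cohorts have no control arm in which the same carry-over would appear, so the analysis cannot separate it out. It would also feed the Section 9.5 interim rule, which stops enrolment when no response is seen.

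The protocol follows the opposite principle elsewhere. Section 8.6.2.2 expects that no tumour treatment was given after collection of a pre-existing biopsy. Criterion 25 requires an archival PD-L1 sample to postdate failure of the last checkpoint-inhibitor line. Criterion 15 keeps irradiated lesions out of the target set unless they have clearly progressed. The baseline scan has no comparable rule for systemic therapy.

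**Working it through.** The plan states no figure for this point, so there is none to reproduce.

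**1. Is there a gap?** Inputs: scan window 28 days (footnote 6); washout W = min(28, 5 × half-life) days (Section 6.5.2). The longest time by which a permitted dose can follow a permitted scan is 28 − W. The gap closes when 5 × half-life = 28, that is, at a half-life of 28/5 = 5.6 days. The documents do not give half-lives of prior drugs, so those below are assumed.

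| Half-life (days) | Washout (days) | Gap (days) |
|---|---|---|
| 0.25 | 1.25 | 26.75 |
| 1 | 5 | 23 |
| 2 | 10 | 18 |
| 4 | 20 | 8 |
| 5 | 25 | 3 |
| 5.6 or more | 28 | 0 |

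For example, a scan on Day −27, a dose on Day −20 and RO7121661 on Day 1 is permitted for a half-life up to 20/5 = 4 days.

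**2. What would be scored?** Let B be the sum on the scan. If the later prior dose reduces it by 30%, the Day 1 sum is 0.70B. With no further change, the week 8 scan meets the partial-response threshold. If the tumour instead grows 20% on study, the sum is 0.70B × 1.20 = 0.84B. That is 16% below B and is scored as stable disease, although a Day 1 baseline would give progression (provided the 5 mm absolute increase is also met). ORR, DCR and PFS can therefore all be affected.

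**3. Which cohorts?**

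- B4: most exposed among the expansion cohorts, through entrants who stopped for intolerance or declined therapy.
- Part A: criterion 3 asks for progression on a cancer therapy, not on the latest one, or accepts those who decline approved therapy.
- B1, B2: criterion 19 says the screening assessment should confirm progression, and exclusion 19 requires 4 weeks from prior anti-PD-1, equal to the scan window.
- B5: participants with a prior metastatic line must have progressed on it (criterion 32).
- B3: no prior therapy for metastatic disease, and adjuvant chemotherapy more than 6 months before Day 1 (exclusions 29 and 30).

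**4. How large?** Added ORR = f × s, where f is the share dosed after the scan and s is the chance that this dose yields a fall of 30% or more. f is not in the documents; assume 5-10%. For s, take the topotecan response rates in Section 2.2.2: 3-6% when progression comes at or soon after first-line therapy, about 25% for later relapse.

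- Low: 0.05 × 0.03 = 0.0015, or 0.15 points.
- High: 0.10 × 0.25 = 0.025, or 2.5 points.

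Cohort size is not in the public text; with an assumed n = 40 this is 0.06 to 1.0 false responders.

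**5. Interim rule.** If RO7121661 were inactive, the chance of at least one carry-over response is 1 − (1 − c)^n with c = f × s. The interim n is not in the public text; for an assumed n = 20, c = 0.15% gives about 3% and c = 2.5% gives 39.7%. For n = 10 and c = 2.5% it is 22.4%. All are before confirmation.

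**The case against.** Three objections carry weight.

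*Confirmation.* The first on-study scan is at week 8, and confirmation comes at the next scheduled visit at least 28 days later (Section 8.1.1), so about week 16 on the 8-weekly schedule. Shrinkage from a Day −20 dose would have to last 20 + 112 = 132 days, about 19 weeks. This stands. Confirmation uses the same baseline and so does not remove the bias, but it makes false responses rarer than step 4 suggests. It gives DCR little protection, because Section 9.4.2 needs stable disease only once, at 4 weeks or more.

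*Entry criteria.* Prior chemotherapy toxicity must have resolved to Grade 1 or lower, with listed exceptions, and blood counts must be adequate (criteria 6 and 7). A cycle given shortly before Day 1 will often conflict with that. This also lowers the frequency, but it does not order the scan after the dose.

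*Purpose.* The study has no hypotheses (Section 9.1), no power or Type I error basis (Section 9.2) and non-binding futility rules (Section 9.5). That limits the consequence of a small bias.

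A reader might infer that all cohorts are equally open to this. They are not, as step 3 shows: in B1, B2 and B5 the scenario generally needs another dose of a failing regimen followed by a marked fall. A reader might also take the Section 2.2.2 statement, "Initial objective response rates of 60 to 80% are seen in patients without substantive co-morbid conditions", as s and reach 0.10 × 0.80 = 8 points. The documents do not support that. The rate describes first-line therapy as a whole, whereas part of the shrinkage would precede the scan and only the remaining dose matters. The 10% is itself an assumption.

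**Conclusion.** The gap exists in the current text: for drugs with a half-life under 5.6 days, a permitted prior dose can follow the baseline scan. It matters mainly in B4 and in Part A, where activity is a secondary objective. On the assumed 5-10% frequency and the 3-25% topotecan rates, ORR would be inflated by about 0.15 to 2.5 points, and by less once confirmation is applied. DCR is more exposed, by an amount the documents do not allow to be estimated. The frequency is unknown, and for someone still responding to first-line chemotherapy s could lie above the range used. The finding does not undermine the design; it supports an inexpensive clarification and one sensitivity analysis.

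**What to change.** Add to Table 1, footnote 6, and mirror in Section 8.10.1 and Appendix 7, Section 1.2.1: a standard-of-care scan may replace the screening scan only if no systemic anti-cancer therapy was given after it; otherwise the scheduled screening scan is done after the last prior dose and as close as possible to Day 1.

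In the analysis, report ORR and DCR with and without participants whose baseline scan preceded their last prior dose. This also covers those already enrolled: prior cancer therapies are collected (Section 8.2.7), and checking the washout already requires the last-dose date.

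The change reduces carry-over but does not remove it, because a scan taken shortly after the last dose still precedes some of that dose's effect. For each responder, therefore, also list the interval from last prior dose to baseline scan.

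The washout rule and the sample size stay as they are. The cost is one sentence in three places, a repeat screening CT for a few participants, one extra table row and one listing column.

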2.1 STUDY RATIONALE

RO7121661, an anti-programmed death-1 (PD-1) / T-cell immunoglobulin and mucin domain 3 (TIM-3) bispecific antibody (BsAb), was designed to target dysfunctional tumor antigen-specific T lymphocytes (expressing PD-1 and TIM-3) in order to establish or reestablish an effective anti-tumor immune-response in cancer patients with high unmet medical need. This may result in improvement in the therapeutic response over currently available therapies and/or overcoming of primary resistance or emerging resistance against PD-1/programmed death-ligand 1 (PD-L1) checkpoint blockade in patients previously treated with PD-1 or PD-L1 checkpoint inhibitors (CPI experienced). Exploration of activity in patients without prior CPI exposure (i.e., CPI naïve) is also planned.

NP40435 is a first in human, open label, multicenter, Phase I study to determine the maximum tolerated dose (MTD) and/or a recommended dose for expansion (RDE) that will allow exploration of the safety, pharmacokinetics (PK), pharmacodynamics (PD), and preliminary anti-tumor activity of RO7121661.

The rationale for the study design is provided in Section 4.3.

2.2 BACKGROUND

Cancer remains a major cause of death worldwide despite several new agents providing survival benefits to patients. Many cancer indications have a poor prognosis, and the management of most advanced solid tumors remains challenging because of the high rate of tumor recurrence or the development of distant metastases.

2.2.1 Non-Small Cell Lung Cancer Patients: Checkpoint Inhibitor Experienced and Naïve

Treatment of patients with advanced non-small cell lung cancer (NSCLC) has undergone significant changes with the development of immune CPI monoclonal antibodies (mAbs) to anti-PD-1/PD-L1 e.g., pembrolizumab, nivolumab or atezolizumab or durvalumab (see recent reviews: Hashimoto et al 2018; Thommen and Schumacher 2018; Zappasodi et al 2018) now commonly used in patients without mutations or rearrangements in the EGFR, ALK and ROS genes. Initial approval was in patients who had prior platinum based chemotherapy. Pembrolizumab approval was supported by the KEYNOTE-001 Phase I trial in patients with ≥50% PD-L1 (Garon et al 2015) and extended by the KEYNOTE-010 Phase III trial in patients with≥1% PD-L1 (Herbst et al 2016). Nivolumab was approved in patients regardless of PD-L1 status, initially in advanced squamous NSCLC (Brahmer et al 2015) and subsequently in non-squamous NSCLC (Borghaei et al 2015). Atezolizumab was approved in patients independent of PD-L1 status and histology (squamous and non-squamous) based on the POPLAR Phase II (Fehrenbacher et al 2016) and the OAK Phase III trials (Rittmeyer et al 2017).

Pembrolizumab has also received approval for treatment-naïve patients with advanced NSCLC without driver mutations and with tumor proportion score (TPS) ≥50% or high tumor PD-L1 expression, based on the KEYNOTE-024 Phase III study (Reck et al 2016). Pembrolizumab also received accelerated approval in combination with platinum and pemetrexed in first line treatment-naïve non-squamous patients irrespective of PD-L1 status based on Phase II results in KEYNOTE-021 (Langer et al 2016) and confirmed in the Phase III KEYNOTE-189 study (Gandhi et al 2018). Recent results from CheckMate 227, a Phase III trial in patients with chemotherapy-naïve stage IV or recurrent NSCLC demonstrates improvement in PFS with first-line nivolumab plus ipilimumab than with chemotherapy among patients with a high tumor mutational burden (TMB), irrespective of PD-L1 expression level. (Hellmann et al 2018) supporting a potential role for the use of TMB as a selection marker for treatment. Furthermore, durvalumab was approved for patients with unresectable Stage III NSCLC based on Phase III results in the PACIFIC study (Antonia et al 2017).

2.2.2 Small Cell Lung Cancer Patients: Checkpoint Inhibitor Naïve

In 2012, the World Health Organization (WHO) estimated the worldwide incidence of new lung cancer cases was 1.8 million, resulting in approximately 1.6 million deaths and accounting for about 13% of total cancer diagnoses (Ferlay et al 2012). In the Western World, approximately 13% of the lung cancers that are diagnosed are small cell lung cancer (SCLC). SCLC occurs primarily in patients with a history of tobacco use and originates from neuroendocrine cell precursors. It is characterized by rapid growth, high response rates to both chemotherapy and radiotherapy, and the development of treatment resistance in patients with metastatic disease (Früh et al 2013).

Although SCLC is more responsive to chemotherapy and radiation therapy than other types of lung cancer, a cure is difficult to achieve because SCLC has a greater tendency to be widely disseminated by the time of diagnosis (NIH National Cancer Institute 2016). At the time of diagnosis, approximately 30% of patients with SCLC will have tumors confined to the hemithorax of origin, the mediastinum, or the supraclavicular lymph nodes. These patients are designated as having limited-stage disease (LD), where the treatment goal is curative (Früh et al 2013). Patients with tumors that have spread beyond the supraclavicular areas are said to have extensive-stage disease (ED). The prognosis of SCLC strongly depends on the tumor stage, which is evaluated by the new tumor-node-metastasis (TNM) version 7 staging system according to the Union for International Cancer Control (UICC) (Früh et al 2013).

In the last 30 years, multiple therapeutic agents and strategies, including dose intensification, have been explored, but with marginal improvement in PFS, and significant toxicity. The most important advances have improved the precision of radiation therapy and have introduced better supportive care measures, such as more effective antiemetic regimens.

The generally accepted standard for first-line systemic therapy is etoposide combined with either cisplatin or carboplatin. Initial objective response rates of 60 to 80% are seen in patients without substantive co-morbid conditions. However, almost all patients with ED and most patients with LD experience disease progression within months of completing first-line therapy.

There is only one approved therapy for SCLC that has progressed on a platinum and etoposide combination regimen: topotecan, a topoisomerase 1 inhibitor. Recurrent/refractory SCLC is substantially less responsive to therapy than primary disease. Response rates for topotecan are approximately 25% for relapses occurring at least 3 months after completion of first-line therapy, and as low as 3 to 6% for progressive disease occurring at the time of or shortly after completion of first-line therapy. Objective responses to a third line of chemotherapy are uncommon.

Recent data demonstrates activity of checkpoint inhibitors in the treatment of SCLC. Two agents, pembrolizumab and atezolizumab, have recently demonstrated activity in both the monotherapy setting in recurrent SCLC and in combination with platinum and etoposide in untreated patients (Chung et al 2018, Ott et al 2017, Horn et al 2018). Monotherapy pembrolizumab demonstrated an ORR of 18.7% in unselected but previously treated SCLC patients and an ORR of 33-35.7% in the PD-L1 positive population (Chung et al 2018, Ott et al 2017). Addition of atezolizumab to platinum chemotherapy as initial therapy has shown a 2 month improvement in overall survival (Horn et al 2018). Although these initial checkpoint inhibitors have demonstrated activity, SCLC remains a major cause of morbidity and mortality worldwide with a significant unmet need for new effective and safe treatments.

